## 13. SAFETY ANALYSES

### 13.1. Adverse Events

Safety will be analyzed principally by examination of the frequency of adverse events. In particular, the primary safety endpoint is the number of lung graft-related serious adverse events (SAEs) up to the 30-day follow-up or until initial hospital admission (if longer than 30 days) after transplantation per subject will be analyzed. This endpoint is defined to consist of the following adverse events (at most one per type), if they are serious adverse events.

- Biopsy proven moderate or severe acute rejection
- Respiratory failure requiring prolonged intubation or reintubation
- Bronchial anastomotic complications
- Major pulmonary-related infection

The primary safety hypothesis is that the mean number of lung graft-related SAEs up to the 30-day follow-up after transplantation is less than a performance goal based on the corresponding mean in the Per-Protocol population of the Control arm of the INSPIRE trial (0.29 events per subject) with a margin of 0.7 events. Specifically:

$$H_{0s}: \mu_{OCS\ Lung} \geq 0.99$$

$$H_{1s}: \mu_{OCS\ Lung} < 0.99$$

where  $\mu_{OCS\ Lung}$  is the mean number of lung graft-related SAEs through 30 days post-transplantation among transplanted recipients.

This endpoint will be summarized using descriptive statistics, specifically the mean, median, standard deviation, minimum, maximum, and a 95% confidence interval for the mean based on the t-distribution. A one-sided one-sample t-test at the 0.025 significance level will be performed to test the null hypothesis,  $H_{0s}$ .

In addition, the numbers and percentages of subjects experiencing at least one adverse event (AE), at least one severe AE, at least one device-related AE (an AE that is probably or definitely related to the investigational device or for which the relationship is missing), at least one unanticipated AE, at least one serious AE, and at least one lung graft-related serious AE, and the number and percentage of deaths will be tabulated. Also, the number and percentage of adverse events and the number and percentage of subjects experiencing adverse events will be tabulated by system organ class (SOC) and preferred term (PT) using MedDRA. A similar analysis will be performed for serious AEs. The number and percentage of AEs will be tabulated by SOC and PT and the relationship of the adverse event to the device (related versus not related, where AEs with a probable or definite relationship to the investigational device are classified as related, and AEs with a possible, unlikely, or unrelated relationship are classified as not related) and by SOC and PT and severity.

The safety analyses will be performed for the Transplanted Recipient Population.

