- **Standard of Care Bronchoscopy & Trans-bronchial Biopsy/Bronchoalveolar Lavage Prior to Discharge (if applicable):** A fiber optic bronchoscopy evaluation may be conducted and recorded prior to initial hospital discharge to assess airway healing and to obtain biopsy samples. A lung biopsy and bronchoalveolar lavage samples may be collected for subsequent evaluation at the investigational sites for acute rejection episodes and infection. If performed, the ISHLT revised rejection grading system will be utilized to evaluate any diagnosed rejection episode according to (see [Appendix 2](#)).

- **Patient and Graft Survival at Day 30 and at Initial Hospital Discharge if Greater than 30 Days:** Patient and graft survival will be assessed and recorded on day 30 post-transplant and at initial hospital discharge if greater than 30 days.
- **Adverse Events:** All serious adverse events and any new lung graft-related adverse events will be followed and documented until the investigator designates the event to be either resolved or its effect on the patient's condition stabilized.
- **Medications:** Medications used to treat all serious adverse event (SAE)-related will be recorded in the trial database until the SAE is resolved.

These follow-ups will be attempted within +2 days of the designated periods except for the PGD scores at T0, T24, T48, and T72 which must be collected on the designated days. The evaluations may be conducted over several days.

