7.3. Long-Term Follow-up: 6, 12, 24, and 36 months (Post-Market Follow-up)

Follow-up data collection will be conducted at approximately 6, 12, 24, and 36 months post-transplant.

- **6, 12, 24, and 36 month Follow Up:** At approximately 6, 12, 24, and 36 months post-transplant, the patient will be evaluated at an office visit if this is the institution's standard of care, and, if not, by phone contact by the site. The patient's medical record will be reviewed to confirm patient's answers. This follow-up will collect the following information on transplanted recipients in the trial:
 - Patient and graft survival
 - Whether the patient was hospitalized after initial discharge, and, if so, the primary reason for the hospitalization and the length of stay; these data will be collected only for the 6-month follow-up timepoint.
 - Clinical diagnosis of BOS and method of diagnosis
 - Results of any standard of care or per-cause pulmonary function tests, bronchoscopies, or biopsies

The 6, 12, 24, and 36 months follow-up will be collected within +30 days of the designated period and will be recorded.

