8.5. Recording and Reporting of Adverse Event

All lung graft-related adverse events and serious adverse events are to be recorded on the case report forms. The description of the adverse event will include the date of onset, duration, severity, seriousness, the relationship of the event to the trial treatment, anticipated or not, and any treatment required. All SAEs will be followed until their resolution.

For all SAEs, the investigator is required to supply any additional data that may be deemed necessary by the Sponsor. Additionally, SAE and unanticipated adverse device effects (UADEs) should be reported to TransMedics, Inc., preferably within 48 hours of the time the investigator learns of the event, but in no case later than 5 working days. For any particular patient, the independent Medical Monitor if required to protect patient safety may specify a different follow-up period. The Sponsor is responsible for the classification and reporting of lung graft-related adverse events to the appropriate regulatory authorities, and for the on-going safety evaluation of the trial in accordance with ISO 14155 and governing regulatory requirements.

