9.6.2. Other Adverse Events

In addition, the numbers and percentages of subjects experiencing at least one lung graft-related AE, at least one severe AE, at least one device-related AE, at least one unanticipated AE, and at least one serious AE, and the number and percentage of deaths will all be tabulated.

The number of adverse events and the number and percentage of subjects experiencing adverse events will be tabulated by system organ class and preferred term using MedDRA. A similar analysis will be performed for serious AEs. The number and percentage of subjects experiencing AEs will also be tabulated by system organ class and preferred term and the relationship of the

adverse event to the device (focusing on differentiating adverse events deemed definitely and probably related to the device). Similar analyses will be performed by the severity of the adverse event.

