APPENDIX 4. SCHEDULE OF CLINICAL ASSESSMENTS

Evaluations	Donor & Lung Assessments	
	At Acceptance	OCS Preservation
Eligibility & ID	X	
Demographics/Characteristics	X	
Donor Cause of Death	X	
Donor Medical History	X	
Initial & Final Blood Gas and PaO ₂ /FiO ₂ Ratio at donor's offer	X	
Ventilation Settings at Final Blood Gas in donor's offer	X	
Final Chest X-ray report/findings	X	
Final Bronchoscopy Findings	X	
Cross Clamp Time and Flush Details		X
Donor Allocation Status		
OCS Pre-Instrumentation ABG (Priming)		X
OCS Instrumentation Details (Date and Time)		X
OCS Preservation Parameters		X
OCS Final Assessment		X
Device Malfunction (if applicable)		X
Non-transplant Reasons (if applicable)		X

Evaluations	Recipient Schedule of Assessments						
	Day of TX	T0	T24	T48	T72	Day 7	Discharge
Eligibility & Informed Consent	X						
Demographic/Characteristics	X						
Etiology of Lung Failure	X						
Medical History including Cardiac	X						
Transplant Details	X						
PGD Scores	X	X	X	X	X		
Mechanical Circulatory Support & Reason	X	X	X	X	X	X	X
Invasive Ventilator Support	X	X	X	X	X	X	X
Patient Survival						X	X
Graft Survival						X	X
Bronchoscopy, BAL & Biopsy					X	X*	X*
Pulmonary Function Test					X**	X*	X*
Immunosuppressive Meds & Induction (if applicable)	X			X	X		
ICU & Hospital Stay	X	X	X	X	X	X	X
Lung Graft-Related SAE's	X	X	X	X	X	X	X
All SAE's & Associated Meds	X	X	X	X	X	X	X
Diagnosis of BOS						X	X

* ONLY tests regularly scheduled per center standard of care or performed due to a clinical cause at these timepoints will be collected.

** Pulmonary Function Test can be done within the first 90 days post transplant according to patient's condition. If not done reason will be specified and recorded.

**APPENDIX 5. DRAFT PATIENT INFORMED CONSENT FORM
TEMPLATE**

(This Page is Intentionally Left Clear)

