## **14. OTHER ANALYSES**

Kaplan-Meier estimated freedom from BOS and BOS-free survival time probabilities will be presented for the following nominal timepoints: Day 30, 6 months, 12 months, 24 months, and 36 months.

Chest radiograph data at transplant and post-transplant timepoints will be summarized using descriptive statistics.

Recipient bronchoscopy data at discharge, 6 months, 12 months, 24 months, and 36 months will be summarized using frequencies and percentages. Transbronchial biopsy results at discharge, 6 months, 12 months, 24 months, and 36 months will be summarized using frequencies and percentages. Recipient pulmonary function test results at discharge (or up to the first 90 days post transplant if not done at discharge), 6 months, 12 months, 24 months, and 36 months will be summarized using descriptive statistics. Recipient data at the 6, 12, 24 and 36 month follow-up visits (was patient withdrawn from the study since the last visit and, if so, the reason for withdrawal, did recipient survive, did the lung graft survive, was there a diagnosis of post-lung transplant Bronchiolitis Obliterans Syndrome since the last visit, was recipient hospitalized since the last follow-up visit) will be summarized using frequencies and percentages.

The number and percentage of patients having mechanical circulatory or ventilator support (i.e., ECMO, any ventilator support, any support) within 30 days post-transplant or until initial discharge (whichever occurs later) will be presented. For each type of support, the table will present descriptive statistics for the time from surgery to the start of the first occurrence of support and for the duration of support. Patients who do not

use a given type of support will be excluded from the analyses for that type of support. If a patient is continuing to use a given type of support at the time of completion / discontinuation, the time of completion / discontinuation will be considered the stop time for that patient for that type of support in calculating the duration of support. If the same support is used multiple times, the duration of support will be the sum of the durations for all periods.

The analyses described above will be performed for the PP and Transplanted Recipient Populations.

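### SAP 13.1 tabulates all adverse events although the protocol directs recording only of serious or graft-related ones, and SAP 14 summarizes hospitalization at three visits where it is not collected

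*SAP*

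**What the plan says.** **Recording.** Protocol 8.5 sets the case report form scope: "All lung graft-related adverse events and serious adverse events are to be recorded on the case report forms". Protocol 7.2 repeats it for the period to Day 30: "All serious adverse events and any new lung graft-related adverse events will be followed and documented". The schedule in Protocol Appendix 4 has one row for lung graft-related serious events and one marked "All SAE's & Associated Meds"; it has no row for all adverse events.

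**Tabulation.** SAP 13.1 will give "the numbers and percentages of subjects experiencing at least one adverse event (AE), at least one severe AE, at least one device-related AE", and also rows for unanticipated, serious and graft-related serious events and for deaths. It then tabulates adverse events by system organ class and preferred term, by relationship and by severity. It adds "A similar analysis will be performed for serious AEs", so the main tables are meant to be wider than serious events. Protocol 9.6.2 opens its list more narrowly, with "at least one lung graft-related AE, at least one severe AE, at least one device-related AE", but its severe, device-related, unanticipated and class/term tables carry no restriction either. SAP 3.5 reports no changes to the protocol-specified analyses.

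**Hospitalization.** SAP 14 lists, among the items summarized at the 6, 12, 24 and 36 month visits, "was recipient hospitalized since the last follow-up visit". Protocol 7.3 says of hospitalization after initial discharge that "these data will be collected only for the 6-month follow-up timepoint".

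**The concern.** A table labelled as all adverse events would hold a filtered subset. Both documents say safety is judged mainly on event frequency, and the trial has a single arm, so no concurrent control shares the under-capture. A reader would take absolute incidence, the severity mix and the device-relatedness profile at face value. The device-related row matters most: Protocol 8.6 has investigators rate relationship to the device, but nothing in 8.5 requires an event to be recorded because it is device-related.

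The SAP also dropped a row that the recorded data can support (graft-related events) and added one that they cannot (any event), without declaring the change. Three of the four hospitalization summaries call for an item that the protocol does not collect at those visits.

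**Working it through.** The documents state no adverse event or hospitalization rate for this trial, so there is no figure to reproduce. The check is a comparison of texts, followed by the direction of the error.

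**1. Which events have a route into the database**

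| Event class | Recording instruction (Protocol 7.2, 8.5) | Needed for the any, severe, device-related, unanticipated and class/term tables |
|---|---|---|
| Serious | Yes | Yes |
| Non-serious, graft-related | Yes (window in 8.1) | Yes |
| Non-serious, not graft-related | None | Yes |

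**2. Whether the third class exists under the protocol's own definitions.** It does.
- Protocol 8.9 makes a clinically significant laboratory change an adverse event.
- Protocol 8.7 defines severe by interference with usual activities, while 8.2 defines serious by outcome. An event can be severe without being serious.
- Protocol 8.6 allows any event to be rated as device-related.

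**3. Direction for the any-event row.** Let q be the share of recipients with at least one recorded event and r the share with at least one third-class event.
- Reported share = q.
- True share, if the two are independent = 1 − (1 − q)(1 − r).
- Shortfall = (1 − q)r, which is never negative.

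Illustration with assumed values, r from 0.3 to 0.9:
- q = 0.50: 0.50 × 0.3 = 0.15 to 0.50 × 0.9 = 0.45, so 15 to 45 points.
- q = 0.90: 0.10 × 0.3 = 0.03 to 0.10 × 0.9 = 0.09, so 3 to 9 points.

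Without independence the shortfall is the share of recipients who have third-class events only. It is zero if every recipient with such an event also has a recorded one. The documents supply neither q nor r. The nearest figure, 13/56 = 23% in Protocol Table 3, comes from the preceding trial and counts four types of graft-related serious event only.

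The same direction holds for every count and every percentage of subjects. SAP 13.1 also plans percentages of events; those can move either way, because their denominator is depleted too.

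**4. What is untouched.** The primary safety endpoint counts four types of serious graft-related event, and all serious events are recorded. The rows for serious events, graft-related serious events and deaths are complete for the same reason.

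**5. Hospitalization.** Planned timepoints: 4 (6, 12, 24, 36 months). Collected: 1 (6 months). Without a source: 4 − 1 = 3. At those three visits the estimate is 0/0. Multiple imputation under SAP 5.3 cannot help, because the item is never observed at those visits. The 6-month summary is unaffected.

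**The case against.** Protocol 7.2 and 8.5 say what must be recorded and do not say that nothing else may be; 7.3, by contrast, does use a limiting word. Section 14.4 has the events committee review every adverse event reported, and the draft case report forms in Appendix 6 are blank, so the actual fields cannot be seen. Appendix 4 is weak support, since it also omits the non-serious graft-related events that 8.1 and 8.5 plainly collect. This stands: total loss of the third class is an inference. Selective capture is still the natural reading, because no section directs that these events be recorded.

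The lost class may also be narrow where it matters most. Seriousness in 8.2 includes prolonging the initial hospital stay, which many severe events in new transplant inpatients would do. The device acts on the donor lung, so most device-related events should also be graft-related. This limits the likely size but does not close the gap.

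Nor is this simply the SAP against the protocol. Protocol 9.6.2 already plans the same unrestricted tables, and only the first row was widened in the SAP.

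A reader might go further and infer that the 12 to 36 month hospitalization rates would come out too low. The documents do not support that. It would require coding an uncollected answer as no, which would give 0/90 if all 90 recipients were counted (exact 95% upper limit 1 − 0.025^(1/90) = 4.0%) whatever the true rate. Neither document says to do this. Re-hospitalizations could in principle surface as serious events under 8.2, but the visit content in 7.3 lists no adverse event collection.

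**Conclusion.** Both mismatches stand on the text.

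- **Adverse events.** Followed as written, the any, severe, device-related and unanticipated rows and the class/term tables would present a subset as if it were complete. Incidence can only be understated. The size cannot be derived from the documents, and the point ranges in the working rest wholly on assumed q and r. The conclusion assumes that sites record what 7.2 and 8.5 direct and no more.
- **Undeclared change.** The SAP's first row is wider than the protocol's, and SAP 3.5 does not say so.
- **Hospitalization.** Three of four planned summaries have no data source and are not estimable.

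The co-primary endpoints, the primary safety endpoint and the mortality and graft-dysfunction stopping rules are not affected. This is an error in the descriptive safety specification that should be corrected; it does not threaten the trial's main tests.

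**What to change.** 1. In SAP 13.1 and Protocol 9.6.2, label the event rows and class/term tables as *serious or lung graft-related adverse events*, and restore the graft-related row in the SAP. If item 2 is adopted, the label should name that class as well.
2. Add a sentence to Protocol 8.5 that any adverse event judged probably or definitely related to the device is recorded whatever its seriousness. Possibly related events are not needed for this row, because SAP 13.1 classes them as not related.
3. Limit the SAP 14 hospitalization summary to the 6-month visit, or remove the 6-month-only limit in Protocol 7.3. The second option uses the contact and chart review already planned at 12, 24 and 36 months.
4. List in SAP 3.5 any difference from the protocol's tables that remains.

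Cost: text edits in both documents, a few more adverse event entries at sites and, under the second option in item 3, one more item at three existing contacts. No new visits or procedures are needed.

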### **3.5. Changes to the Protocol-Specified Analyses**

Not applicable.

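### For the device-relationship tables of adverse events, and by natural reading the severity tables, SAP 13.1 counts events where Protocol 9.6.2 counts subjects, and SAP 3.5 declares no change

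*SAP*

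**What the plan says.** **Protocol 9.6.2 (Other Adverse Events).** The relationship table is defined by subject: "The number and percentage of subjects experiencing AEs will also be tabulated by system organ class and preferred term and the relationship" to the device. The paragraph then adds: "Similar analyses will be performed by the severity of the adverse event".

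**SAP 13.1 (Adverse Events).** The same table is defined by event: "The number and percentage of AEs will be tabulated by SOC and PT and the relationship of the adverse event to the device". The sentence goes on to cover severity, "and by SOC and PT and severity", with AEs still the thing being counted. The SAP does not say what the percentage is a percentage of.

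**SAP 3.5.** Under the heading "3.5. Changes to the Protocol-Specified Analyses" the entry is "Not applicable".

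**What SAP 13.1 still reports by subject.** There are overview rows for recipients with any AE, any severe AE, any device-related AE, any unanticipated AE, any serious AE and any lung graft-related serious AE. There are also subject-level SOC/PT tables for all AEs and for serious AEs. None of those SOC/PT tables is split by relationship or severity.

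**The concern.** The two documents define the same displays with different units, and the SAP says that nothing has changed. The trial has a single arm and no concurrent control, so the share of recipients who had a device-related or a severe event of a given type is basic descriptive safety evidence. The protocol commits to reporting it. A share of events answers a different question. It moves with the frequency of other events, and it does not distinguish one recipient with repeated events from several recipients with one each. The resulting tables also could not be set beside the protocol's own summary of EXPAND I (Table 3), which is by subject.

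**Working it through.** **1. Is the change of unit deliberate or loose wording?** Just before the relationship sentence, SAP 13.1 lists events and subjects as two separate items for the plain SOC/PT table. The SAP therefore distinguishes the units and, for relationship and severity, names only events.

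**2. Does the protocol's severity analysis use subjects?** It is described only as similar to what precedes it. Two antecedents are possible: the relationship table (subjects) or the plain SOC/PT table (events and subjects). Both include subjects. This is the natural reading, but the severity sentence does not name the unit.

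**3. Can the missing figures be recovered from other SAP tables?** The overview rows have relationship and severity but no event type. The subject-level SOC/PT tables have event type but neither relationship nor severity. In general the cross-classification cannot be rebuilt from these margins.

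**4. How do the two percentages relate?** Let n be all subjects, E all AEs, s the subjects with an event in a category and e the events in it. If the event percentage is taken over all AEs (an assumption, because the SAP states no denominator), then

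subject % ÷ event % = (s/n) ÷ (e/E) = (E/n) × (s/e).

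**5. Check against the protocol's own figures (section 1.4.4, Table 3; 56 subjects, 14 lung graft-related serious AEs).** The subject basis reproduces: 13/56 = 23.2%, 11/56 = 19.6% and 3/56 = 5.4%, printed as 23%, 20% and 5%. With the 14 events as denominator:

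| Event type | Subject % | Event % | Ratio |
|---|---|---|---|
| Respiratory failure | 11/56 = 19.6% | 11/14 = 78.6% | 0.25 |
| Major pulmonary infection | 3/56 = 5.4% | 3/14 = 21.4% | 0.25 |

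The ratio is E/n = 14/56 = 0.25, because each affected subject has one event per type. Here the event percentage is four times the subject percentage.

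**6. Range for this trial.** The documents give no expected number of AEs per recipient, so E/n is varied as an assumption. Take n = 90 and a category with 12 events, one per affected recipient, so that subject % = 12/90 = 13.3%:

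| AEs per recipient | Event % = 12/(90 × E/n) | Subject % ÷ event % |
|---|---|---|
| 0.25 | 53.3% | 0.25 |
| 1 | 13.3% | 1 |
| 2 | 6.7% | 2 |
| 3 | 4.4% | 3 |
| 5 | 2.7% | 5 |
| 8 | 1.7% | 8 |

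With two events per affected recipient (6/90 = 6.7% of subjects), every ratio halves. The event percentage is the smaller one only when (E/n) × (s/e) exceeds 1.

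**7. A consequence that does not depend on AE frequency.** Six device-related events of one type in one recipient (1/90 = 1.1% of subjects) and one such event in each of six recipients (6/90 = 6.7%) give the same event cell for any fixed AE total. At an assumed 5 AEs per recipient that cell is 6/450 = 1.3% in both cases.

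**The case against.** The strongest reply is that these are secondary descriptive tables. They have no test attached and no bearing on the primary safety endpoint, the co-primary endpoints or the stopping rules. Subject-level reporting also survives in the overview rows and the SOC/PT tables, and SAP 5.1 puts all collected data in listings. All of this stands. It limits the weight of the point but does not supply the missing split. In the six-event example, neighbouring tables would reveal the difference if those were the only events of that PT or the only device-related events, but not otherwise.

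Three stronger readings are tempting, and the documents support none of them.

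- **That the SAP's percentages will be several times smaller and so flatter the device.** A ratio of 3 needs at least 3 AEs per recipient with one event per affected recipient, or at least 6 with two. Neither document gives such a count. Protocol 8.5 requires only lung graft-related AEs and serious AEs on the case report forms, so the count could be low, although sections 8.9 and 14.4 read more widely. The EXPAND I figures go the other way, but they cover only the graft-related serious subset and do not settle the direction for all AEs. If the SAP's denominator were the events within a PT, the figures in steps 6 and 7 would not arise at all.
- **That the SAP contradicts the protocol by merging definite and probable.** The protocol's phrase, "focusing on differentiating adverse events deemed definitely and probably related to the device", can mean separating the two classes from each other or separating them jointly from the rest. The SAP does the latter.
- **That per-recipient risk disappears from the report.** It does not. Only the split by event type within relationship and within severity is lost.

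**Conclusion.** The inconsistency is real and undeclared. It is explicit for device relationship and follows by natural reading for severity. Its effect is that no planned table gives the share of recipients with a device-related, or a severe, event of a given type. The numerical gap between event and subject percentages cannot be fixed from the documents. It may go in either direction, from a ratio of 0.25 in the EXPAND I subset to 8 at an assumed 8 AEs per recipient with one event per affected recipient. Those ratios assume that all AEs in the set form the denominator. The point should be corrected before analysis, but it concerns descriptive safety tables only and no inferential conclusion depends on it.

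**What to change.** In SAP 13.1, rewrite the relationship and severity sentence so that both tables show the number and percentage of subjects alongside the number of events:

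- by SOC, PT and relationship, with each subject counted once per SOC and PT at the closest relationship;
- by SOC, PT and severity, with each subject counted once per SOC and PT at the highest severity;
- with the Transplanted Recipient Population, already the SAP's safety population, as the percentage denominator.

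The once-per-subject rule is in neither document. It is proposed here so that no recipient is counted twice within a row. Showing definite and probable separately as well as combined is optional and would satisfy either reading of the protocol.

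If the sponsor prefers event-based tables, SAP 3.5 should declare and justify the departure, and SAP 13.1 should state the denominator.

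The cost is one more set of columns in two tables. No new data are needed. The reported percentages may turn out larger or smaller than the event-based ones.
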